For example, among subjects HPV 16 seronegative and PCR positive at Day 1 or HPV 18 seronegative and PCR positive at Day 1, the incidence of CIN 2/3 related to the relevant HPV type will be estimated in each treatment group and the 95% confidence intervals for these rates will be provided. Only cases of CIN that are detected following the Month 7 visit will be included in this analysis.

j. Assessment of Potential Waning of Vaccine Efficacy

Due to the timing between the development of HPV infection and the development of clinical sequelae, it is expected that the target number of cases required to estimate the vaccine efficacy with respect to the primary endpoint of the study at the interim analysis (19 cases) will be observed ~2.5 years into the study. By Year 4, it is anticipated that ~10 to 12 additional cases will be observed. Thus, there is limited power in this study to draw any definitive conclusions regarding changes in vaccine efficacy over time. Nevertheless, an exploratory analysis will be conducted to assess a possible waning of the vaccine efficacy. Specifically, at the conclusion of the study, the vaccine efficacy by year will be estimated, and any observed trends in the efficacy over time will be reported. The first year estimate will include all follow-up through Month 12 for each subject; the second year estimate will include all follow-up through Month 24 for each subject; the third year estimate will include all follow-up through Month 36 for each subject; and the final estimate will include all follow-up through Month 48 for each subject. A potential waning of vaccine efficacy will be explored using the per-protocol and first MITT populations.

D. Definition of Compliance Measure

Treatment compliance is defined in this study as receipt of all scheduled study vaccinations. To summarize treatment compliance, the numbers of subjects who receive each vaccination will be tabulated by treatment group. As stated in Section III.B., subjects who do not complete the full vaccination regimen will be excluded from the per-protocol primary analyses of efficacy but will be included in 2 MITT analyses.

Another important compliance measure in this study is the degree of subject compliance with follow-up visits following the completion of the vaccination series. Since colposcopy is a required procedure for the identification of potential study endpoints, subjects who miss study follow-up visits or who

D. Definition of Compliance Measure (Cont.)

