In the primary per-protocol analysis, follow-up for CIN 2/3 and cervical cancer begins following the Month 7 visit. Therefore, each subject's follow-up time will be computed by calculating the number of days between her Month 7 visit date and her final visit date. For cases, the "final visit" will be the first visit at which CIN 2/3 or cervical cancer was detected for the purpose of person-time computation. This value will be converted to person-years by dividing by 365.25. To obtain the total follow-up time in each treatment group, k_v and k_p , the person-years will be summed over all subjects in the given treatment group.

Although the primary analysis is per-protocol and HPV type-specific, all subjects who are eligible for the per-protocol analysis based on at least 1 of the 2 HPV types being analyzed (HPV 16 or 18) will contribute follow-up time to the totals. For the exploratory analysis of all CIN 2/3, all subjects who are eligible for the per-protocol analysis based on at least 1 high-risk HPV type will contribute follow-up time to the totals.

d. Correlates of Protection

In addition to the methods described in Section III.C.3.c. for assessing the anti-HPV serum RIA responses as potential correlates of protection, the odds of developing breakthrough HPV 16/18-related CIN 2/3 or worse may be modeled as a function of the corresponding Postdose 3 RIA titers using a logistic regression model. Length of postvaccination follow-up and study site will be included as additional model terms. Statistical significance of the coefficient for the RIA titer will be an indication that RIA titer is a predictor of breakthrough

D. Statistical Methods (Cont.)

infection. The estimate of the coefficient will indicate the nature of the relationship. If there are few cases among the vaccine recipients, there may be insufficient information to establish an immune correlate of protection in this study.

e. Potential Bias**1) Ascertainment Bias**

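### The waning analysis in SAP III.C.3.j labels cumulative efficacy as efficacy by year, which dilutes and delays a late loss of protection

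*SAP*

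**What the plan says.** SAP Section III.C.3.j states its aim as follows: "the vaccine efficacy by year will be estimated, and any observed trends in the efficacy over time will be reported". It then fixes four windows, each open from the start of follow-up. The earliest closes at Month 12. Of the next it says: "the second year estimate will include all follow-up through Month 24 for each subject". Another, built in the same way, closes at Month 36. Of the last the section says: "the final estimate will include all follow-up through Month 48 for each subject".

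The analysis is to be run in the per-protocol and first MITT populations. The section calls it exploratory and concedes limited power. On timing, it expects that the target number of cases "at the interim analysis (19 cases) will be observed ~2.5 years into the study", and adds: "By Year 4, it is anticipated that ~10 to 12 additional cases will be observed". Section VII.D.1.c sets the start of the clock for the per-protocol analysis: "follow-up for CIN 2/3 and cervical cancer begins following the Month 7 visit".

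No section gives efficacy for a single period, a treatment-by-time term or a time-varying hazard ratio. Section III.C.3.c plans Kaplan-Meier curves and a log-rank test for the primary endpoint.

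**The concern.** The stated quantity (efficacy in each year) and the specified quantity (efficacy from Month 7 up to a given month) differ within one paragraph. Each later window contains all the earlier ones, so successive estimates share cases and person-time and are correlated. The fourth covers the whole planned follow-up, so it repeats the overall study estimate under a yearly label.

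A reader who takes the fourth figure as protection in the last year will overstate late efficacy if protection has fallen. That matters because Sections VI.A and VII.C give longer-term efficacy as a reason to continue the study after a successful interim analysis, and III.C.3.j is the section specified to look at efficacy over time.

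**Working it through.** **The SAP's method and its own figures.** III.C.3.j gives no power or precision figure, so the nearest check is Table 7, which rests on the exact conditional method of VII.D.1.a. With equal follow-up, the vaccine share of cases is p = (1 - VE)/(2 - VE), and the test rejects when P(X ≤ c | T, 0.5) ≤ α/2. This gives c = 4 of 19 and c = 8 of 29.

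| Cases, two-sided α | True VE | Recomputed power | Table 7 |
|---|---|---|---|
| 19, 0.0204 | 80 / 85 / 90% | 80.1 / 90.9 / 97.6% | 80 / 90 / 97% |
| 29, 0.0411 | 80 / 85 / 90% | 95.9 / 99.1 / 99.9% | 95 / 99 / >99% |

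Agreement is within one percentage point, so the method is read correctly.

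**Window lengths.** From Month 7, follow-up through Months 12, 24, 36 and 48 holds 5, 17, 29 and 41 months. The disjoint pieces are 5, 12, 12 and 12 months.

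**Cumulative against interval efficacy.** Assume a constant placebo hazard, no attrition and equal person-time per arm. Then cumulative VE = 1 - Σ[months × (1 - interval VE)] / Σ months.

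- 95/95/95/50%: 1 - (29 × 0.05 + 12 × 0.50)/41 = 1 - 7.45/41 = 81.8%.
- 95/95/95/0%: 1 - (29 × 0.05 + 12 × 1)/41 = 1 - 13.45/41 = 67.2%.
- 95/95/70/40%: at Month 36, 1 - (17 × 0.05 + 12 × 0.30)/29 = 1 - 4.45/29 = 84.7%; at Month 48, 1 - (4.45 + 12 × 0.60)/41 = 1 - 11.65/41 = 71.6%.

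| True VE by interval | Reported through M12 | M24 | M36 | M48 |
|---|---|---|---|---|
| 95 / 95 / 95 / 50% | 95% | 95% | 95% | 82% |
| 95 / 95 / 95 / 0% | 95% | 95% | 95% | 67% |
| 95 / 95 / 70 / 40% | 95% | 95% | 85% | 72% |

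**Sensitivity to case timing.** Suppose placebo cases instead follow the SAP's expected pattern: 19 by about Month 30 and 10 more by Month 48, evenly spread within each stretch. The last year then holds 10 × 12/18 = 6.67 of 29 placebo cases (23%, against 12/41 = 29% above). The final figure is 1 - (22.33 × 0.05 + 6.67 × 0.50)/29 = 85% when last-year VE is 50%, and 1 - (22.33 × 0.05 + 6.67)/29 = 73% when it is 0%. Dilution is somewhat stronger.

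**With whole cases.** Take the SAP's counts with assumed splits between arms (vaccine:placebo): the first 19 cases 1:18 and the next 10 cases 5:5. Efficacy after about Month 30 is 0% (95% CI -335% to 77%). The cumulative estimate through Month 48 is 1 - 6/23 = 74% (34% to 91%). With 12 later cases split 6:6 it is 1 - 7/24 = 71% (30% to 89%).

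**Price of disjoint intervals.** Ten late cases split 0:10 give VE 100% with a lower 95% bound of 55%. A 1:9 split gives 89% with a lower bound of 20%.

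**A trend model.** At 95% VE, expected vaccine cases among 29 are 29 × 0.05/1.05 = 1.4, and the chance of none is (1/1.05)^29 = 24%. With none, a treatment-by-time term cannot be estimated.

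**The case against.** The SAP presents this as an exploratory look with limited power, and no test, alpha or submission decision rests on it. That stands and limits the severity. It does not settle the matter, because low power concerns precision, whereas nested windows make the later figures estimate something other than efficacy in that year, whatever the number of cases.

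The Kaplan-Meier curves would show late vaccine-arm cases at their event times. That also stands, but the curves give no efficacy by period. If cases and person-years were tabulated by arm for each window, a reader could subtract one window from the next. The section does not promise that table, and intervals for the differences would still be missing.

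A reader might infer that the series would look near-stable and hide a late loss altogether. The figures do not support that: 95% to 82%, or to 67%, is a visible drop, and the section commits to reporting observed trends. A reader might also expect 29 × 5/41 = 3.5 cases in the first interval and 29 × 12/41 = 8.5 in each later one. That puts all 29 cases on placebo at a constant hazard. The SAP gives no counts by year or arm, and its remark on the lag from infection to disease makes several cases by Month 12 doubtful.

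**Conclusion.** The point holds as a mismatch between aim and definition. III.C.3.j promises efficacy by year and specifies cumulative efficacy, so a late loss appears smaller and later than it is. A last-year efficacy of 50% after 95% would be reported as about 82% (85% under the SAP's case timing), and of 0% as about 67% (73%). These sizes rest on assumed waning patterns, equal person-time and no attrition; the first of each pair also assumes a constant placebo hazard. The nesting itself rests on the text alone. The primary hypothesis test is untouched and the analysis is exploratory, so the severity is minor.

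**What to change.** In III.C.3.j:

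1. Estimate VE in disjoint intervals (Months 7-12, >12-24, >24-36, >36-48), using only the cases and person-years at risk in each, tabulated by arm, with the exact conditional interval of VII.D.1.a.
2. Prespecify a rule for merging adjacent intervals when cases are sparse.
3. Assign a case found through a scheduled visit's Pap triage to the interval ending at that visit, in both arms. Scheduled Pap tests fall at Months 12, 24, 36 and 48 and the biopsy follows, so cutting at tissue date would move a visit's cases into the next interval.
4. Keep the present series as a supplement, labelled cumulative.
5. Treat a treatment-by-time term as optional, only if vaccine-arm cases permit.

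The cost is a revised paragraph and one table, with no new data and no alpha. The drawback is wide intervals, and merging may leave only two or three periods.

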To evaluate the persistence of vaccine-induced serum anti-HPV 6, anti-HPV 11, anti-HPV 16 and anti-HPV 18 responses, GMTs and the proportions of subjects with anti-HPV ≥ 200 mMU/mL for each vaccine HPV type will be summarized at Month 7, Month 24, and Month 48. Graphical displays of the distribution of titers among subjects administered each lot of the quadrivalent HPV (Types 6, 11, 16, 18) L1 VLP vaccine will be provided by HPV type.

C. **Approaches to Immunogenicity Analysis (Cont.)**

3. **Exploratory Immunogenicity Analyses**

a. **Immune Responses to Each Vaccine HPV Type in Subjects Who Are Baseline Seropositive for the Given Type**

Assessments in this section will be performed only when data permits; that is, when the number of subjects in the subgroup being analyzed is sufficient.

To explore a potential association between baseline seropositivity for a given vaccine HPV type and improved Postdose 3 immunogenicity for the same HPV type (immune memory), the proportions of subjects with anti-HPV ≥ 200 mMU/mL and the GMTs at Month 7 for each vaccine HPV type will be summarized in subjects who are seropositive at Day 1 for that vaccine HPV type (6, 11, 16, or 18), regardless of PCR status. The responses will be compared observationally with the proportions of subjects with anti-HPV ≥ 200 mMU/mL and the GMTs at Month 7 in (1) subjects who are seronegative at Day 1 and PCR-negative from Day 1 through Month 7 for the vaccine HPV type of interest and (2) subjects who are seronegative at Day 1 and PCR-negative from Day 1 through Month 7 for all vaccine types. RCDF (Reverse Cumulative Distribution Function) plots will also be used to observationally compare these groups. These summaries will evaluate the anamnestic responses to the individual components of the quadrivalent HPV (Types 6, 11, 16, 18) L1 VLP vaccine. Table 2 outlines the groups that will be compared for this analysis.

Table 2

Comparisons to Assess a Potential Association Between Baseline Seropositivity and Improved Immunogenicity at Month 7

Comparison Group 1	Comparison Group 2
HPV type 6 sero+ at Day 1 [†]	HPV type 6 naïve [‡]
HPV type 6 sero+ at Day 1 [†]	Naïve for all vaccine HPV types [‡]
HPV type 11 sero+ at Day 1 [†]	HPV type 11 naïve [‡]
HPV type 11 sero+ at Day 1 [†]	Naïve for all vaccine HPV types [‡]
HPV type 16 sero+ at Day 1 [†]	HPV type 16 naïve [‡]
HPV type 16 sero+ at Day 1 [†]	Naïve for all vaccine HPV types [‡]
HPV type 18 sero+ at Day 1 [†]	HPV type 18 naïve [‡]

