HPV type 18 sero+ at Day 1 [†]	Naïve for all vaccine HPV types [‡]
Comparisons will be made between Group 1 and Group 2.	
Sero+ = Seropositive.	
[†] Regardless of PCR status.	
[‡] Naïve = Seronegative at Day 1 and PCR negative from Day 1 through Month 7.	

C. Approaches to Immunogenicity Analysis (Cont.)

To investigate whether or not the baseline titer of a subject who is seropositive at Day 1 for a given vaccine HPV type has an impact on the subject's response to the vaccine at Month 7, the natural log of the Month 7 titers for a given HPV type will be modeled as a function of treatment group and the natural log of the baseline HPV titer for that same HPV type for subjects who are seropositive for that HPV type at baseline. Three regression models will be constructed. The first will be a linear regression model with the natural log titers at Month 7 as the response variable. The second will be a logistic regression model with an indicator of whether or not the subject's Month 7 titer is ≥ 200 mMU/mL as the response variable. The third will be a linear regression model with the difference in natural log titer between Month 7 and Day 1 as the response variable (this model is equivalent to modeling the fold-rise in titer from Day 1 to Month 7).

The study will also explore whether subjects who are HPV infected but who do not have detectable anti-HPV at baseline have an active immune response to the infection. In particular, peak (Month 7) and persistence anti-HPV responses for a given vaccine HPV type will be compared between subjects who are infected at Day 1 (PCR positive) with that HPV type, but who have not developed a detectable anti-HPV response (seronegative) to that type, and those who are naïve for that HPV type. It is assumed that newly infected subjects are PCR positive but still have negative RIA titers. Therefore, the antibody responses in subjects who are initially PCR positive but seronegative for a given vaccine HPV type will be summarized and compared observationally with subjects who are HPV-naïve for that HPV type and with subjects who are HPV-naïve for all vaccine HPV types (naïve implies seronegative at Day 1 and PCR-negative from Day 1 through Month 7). The GMTs and the proportions of subjects with anti-HPV ≥ 200 mMU/mL at Month 7 and through the persistence phase will be summarized. Table 3 outlines the groups that will be compared for this analysis.

C. Approaches to Immunogenicity Analysis (Cont.)

Table 3

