**Comparisons to Explore Implied Immunity
in Subjects With New HPV Infections**

Comparison Group 1	Comparison Group 2
HPV type 6 PCR+ and sero- at Day 1	HPV type 6 naïve [†]
HPV type 6 PCR+ and sero- at Day 1	Naïve for all vaccine HPV types [†]
HPV type 11 PCR+ and sero- at Day 1	HPV type 11 naïve [†]
HPV type 11 PCR+ and sero- at Day 1	Naïve for all vaccine HPV types [†]
HPV type 16 PCR+ and sero- at Day 1	HPV type 16 naïve [†]
HPV type 16 PCR+ and sero- at Day 1	Naïve for all vaccine HPV types [†]
HPV type 18 PCR+ and sero- at Day 1	HPV type 18 naïve [†]
HPV type 18 PCR+ and sero- at Day 1	Naïve for all vaccine HPV types [†]
Comparisons will be made between Group 1 and Group 2. PCR+ = PCR positive. Sero- = Seronegative. [†] Naïve = Seronegative at Day 1 and PCR negative from Day 1 through Month 7.	

To assess the difference between subjects who may have natural immunity (subjects who are initially seropositive but PCR negative) and subjects with persisting immune responses after natural infection, GMTs will be summarized and compared at Month 7 between subjects who are initially seropositive and PCR positive for a given vaccine HPV type and subjects who are initially seropositive but PCR negative for that type. These summaries will allow an observational assessment of the differences in RIA titers between the 2 groups. Table 4 lists the groups that will be compared for this analysis.

Table 4

**Comparisons to Assess the Difference Between Subjects With
Probable Natural Immunity and Subjects With Persisting Immune
Responses After Natural Infection**

Comparison Group 1	Comparison Group 2
HPV type 6 sero+ and PCR+ at Day 1 [†]	HPV type 6 sero+ but PCR- at Day 1 [†]
HPV type 11 sero+ and PCR+ at Day 1 [†]	HPV type 11 sero+ but PCR- at Day 1 [†]
HPV type 16 sero+ and PCR+ at Day 1 [†]	HPV type 16 sero+ but PCR- at Day 1 [†]
HPV type 18 sero+ and PCR+ at Day 1 [†]	HPV type 18 sero+ but PCR- at Day 1 [†]
Comparisons will be made between Group 1 and Group 2. Sero+ = Seropositive. PCR+ = PCR positive. PCR- = PCR negative. [†] HPV seronegative at Day 1 and PCR negative from Day 1 through Month 7 for all other vaccine HPV types.	

C. Approaches to Immunogenicity Analysis (Cont.)**b. Association Among Vaccine HPV Types**

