The exploratory analysis of the association among vaccine HPV types has 2 goals: (1) to ascertain if seropositivity for one HPV type impacts the immune response to another vaccine HPV type and (2) to assess whether or not the magnitude of the association appears to increase by the number of other vaccine HPV types for which the subject is positive.

To assess whether or not baseline seropositivity for 1 vaccine HPV type impacts the immune response to another vaccine HPV type, the GMTs and the proportions of subjects with anti-HPV ≥ 200 mMU/mL at Month 7 for a given vaccine HPV type will be observationally compared between subjects who are HPV naïve for all vaccine HPV types from Day 1 to Month 7 and subjects who are HPV naïve for the given vaccine HPV type but seropositive for each 1 of the other 3 vaccine HPV types individually. For example, the HPV 6 immune responses will be summarized and compared between subjects who are HPV naïve for all vaccine HPV types from Day 1 to Month 7 and: (1) subjects who are naïve for HPV type 6 from Day 1 to Month 7 but seropositive to HPV type 11 at Day 1; (2) subjects who are naïve for HPV type 6 from Day 1 to Month 7 but seropositive to HPV type 16 at Day 1; and (3) subjects who are naïve for HPV type 6 from Day 1 to Month 7 but seropositive to HPV type 18 at Day 1. RCDF plots will also be used to compare these groups. Table 5 outlines the groups that will be compared for this analysis.

C. Approaches to Immunogenicity Analysis (Cont.)

Table 5

Comparisons to Assess the Impact of Baseline Seropositivity for One Vaccine HPV Type on the Immune Responses to Another Vaccine HPV Type

HPV Type to be Summarized	Comparison Group 1	Comparison Group 2
6	Baseline sero+ for HPV type 11 [†] Baseline sero+ for HPV type 16 [†] Baseline sero+ for HPV type 18 [†]	Vaccine HPV type naïve [‡] Vaccine HPV type naïve [‡] Vaccine HPV type naïve [‡]
11	Baseline sero+ for HPV type 6 [†] Baseline sero+ for HPV type 16 [†] Baseline sero+ for HPV type 18 [†]	Vaccine HPV type naïve [‡] Vaccine HPV type naïve [‡] Vaccine HPV type naïve [‡]
16	Baseline sero+ for HPV type 6 [†] Baseline sero+ for HPV type 11 [†] Baseline sero+ for HPV type 18 [†]	Vaccine HPV type naïve [‡] Vaccine HPV type naïve [‡] Vaccine HPV type naïve [‡]
18	Baseline sero+ for HPV type 6 [†] Baseline sero+ for HPV type 11 [†] Baseline sero+ for HPV type 16 [†]	Vaccine HPV type naïve [‡] Vaccine HPV type naïve [‡] Vaccine HPV type naïve [‡]

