- d. all subjects followed beyond Month 7 are eligible to be endpoints and any subject who discontinues the study is at risk for HPV 16- or 18-related CIN 2/3 or worse for half of the study;
- e. the incidence of CIN 2/3 or worse related to HPV Type 16 will be ~0.19% in the placebo group over the 41 months after Postdose 3, while the incidence of CIN 2/3 or worse related to HPV Type 18 will be ~0.038% in the placebo group over the 41 months after Postdose 3; and
- f. if the vaccine efficacy is extremely high, all cases will have to accrue in the placebo group before the efficacy analysis may be performed.

A. Planned Statistical Power and Sample Size (Cont.)

[figure not shown]
Assuming that all subjects followed beyond Month 7 are eligible to be considered as endpoints, a sample size of 11,500 will provide ~8000 subjects who are eligible to be considered as cases according to the HPV 16-related disease definition and ~8000 subjects who are eligible to be cases according to the HPV 18-related disease definition. Since the primary endpoint is a composite endpoint, any subject who is eligible to be considered as an endpoint according to the HPV 16-related disease definition, the HPV 18-related disease definition or both will be included in the population at risk for the primary analysis. Therefore, assuming an ~8% overlap in the number of subjects who are HPV 16 or 18 seropositive at Day 1 or PCR positive Day 1 through Month 7, the population at risk for the primary analysis will include ~9000 subjects. Using a person time approach under assumptions (3) and (4) and given the event rates in assumptions (5) and (6), ~9000 subjects in the population at risk will provide the required number of endpoints by Year 4 of the study.

Figures 1 and 2 illustrate the derivation of the HPV 16-related CIN 2/3 cases and HPV 18-related CIN 2/3 cases, respectively, from the 11,500 subjects enrolled.

A. Planned Statistical Power and Sample Size (Cont.)

Figure 1

[figure not shown]
Derivation of HPV 16-Related CIN 2/3 Cases

A. Planned Statistical Power and Sample Size (Cont.)

Figure 2

Derivation of HPV 18-Related CIN 2/3 Cases

A. Planned Statistical Power and Sample Size (Cont.)**2. Immunogenicity (Consistency Lot Substudy)**

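### Exploratory Tables 2 and 3 leave Group 1 unrestricted on the other three vaccine HPV types, so a difference in Month 7 GMT mixes own-type and other-type status

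*SAP*

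**What the plan says.** All of this concerns exploratory immunogenicity in the SAP, Section IV.C.3.

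- **Table 2, Group 1:** women "seropositive at Day 1 for that vaccine HPV type (6, 11, 16, or 18), regardless of PCR status". The only footnote on this group is "Regardless of PCR status".
- **Table 3, Group 1:** women PCR positive and seronegative at Day 1 for the type. No footnote is attached to this group.
- **Comparators in both tables:** (1) Day 1 seronegative women who are "PCR-negative from Day 1 through Month 7 for the vaccine HPV type of interest", with the other types left free; (2) Day 1 seronegative women who are "PCR-negative from Day 1 through Month 7 for all vaccine types".
- **Planned use:** for Table 2 the plan says: "These summaries will evaluate the anamnestic responses to the individual components". Table 3 explores whether infected women without detectable antibody have an active response to the infection.
- **Tables 4 and 5:** both carry a footnote that fixes the remaining types: "HPV seronegative at Day 1 and PCR negative from Day 1 through Month 7 for all other vaccine HPV types".
- **Section IV.C.3.b:** its first goal is "to ascertain if seropositivity for one HPV type impacts the immune response to another vaccine HPV type".

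The plan describes all these group comparisons as observational and makes them conditional on sufficient numbers.

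**The concern.** Table 2 is meant to show own-type immune memory, and Table 3 an own-type response in new infections. Women positive for one vaccine type may also be positive for others more often than the women they are compared with. If positivity for another type changes the response to the type being summarised, Group 1 would differ from its comparator even with no own-type effect at all.

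The plan does not assume such an effect away; it sets out to look for it in IV.C.3.b. It also has the safeguard to hand, since Tables 4 and 5 use it, and gives no reason for leaving it out of Tables 2 and 3. At stake is how the memory and implied-immunity summaries in the study report are interpreted. No hypothesis test depends on them.

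**Working it through.** **1. Set the definitions side by side.**

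| Comparison | Other-type status in Group 1 | Other-type status in Group 2 |
|---|---|---|
| Tables 2 and 3, type-naive rows | free | free |
| Tables 2 and 3, all-naive rows | free | fixed negative |
| Table 4 | fixed negative | fixed negative |
| Table 5 | fixed negative, apart from the one named type | fixed negative |

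In the all-naive rows the groups differ in own-type and other-type status together. In the type-naive rows they are balanced on other types only if positivity for different types is unrelated.

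**2. Is it unrelated on the plan's own figures?** The only pair with figures is HPV 16 and 18. Section VII.A.1 takes 18% positive for HPV 16, 18% for HPV 18 and 15% attrition to Month 7, "assuming an ~8% overlap in the number of subjects who are HPV 16 or 18 seropositive at Day 1 or PCR positive Day 1 through" (the period runs to Month 7).

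First check that the 8% means positive for both types, by reproducing the plan's totals:

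- Eligible per type: 11,500 × 0.85 × 0.82 = 8,016 (plan: about 8,000).
- Population at risk: 11,500 × 0.85 × (1 − 0.08) = 8,993 (plan: about 9,000).

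Both agree. Independence would give 0.18 × 0.18 = 3.2% positive for both, and 9,458 at risk, so the plan itself assumes clustering. Then:

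- HPV 18 positive among HPV 16-positive women: 8/18 = 44.4%.
- HPV 18 positive among HPV 16-negative women: (18 − 8)/(100 − 18) = 12.2%.
- HPV 18 positive among all-naive women: 0%.

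**3. What false ratio could follow?** Suppose there is no own-type effect and HPV 18 positivity multiplies the anti-HPV 16 GMT by F. The observed ratio is then F raised to the difference in the HPV 18-positive share: 0.322 against type-naive women and 0.444 against all-naive women. The plan gives no F, so a range is shown.

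| Assumed F | Against type-naive | Against all-naive |
|---|---|---|
| 1.25 | 1.07 | 1.10 |
| 1.5 | 1.14 | 1.20 |
| 2 | 1.25 | 1.36 |

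**4. Compare with sampling error.** The substudy has 1,500 × 0.85 = 1,275 vaccine recipients at Month 7. Of these, 18% is about 230 HPV 16-positive women, leaving about 1,045 who are not. With the SD of 1.2 on the natural log scale from Section VII.A.2, assumed to hold here:

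- SE = 1.2 × √(1/229.5 + 1/1,045.5) = 0.087.
- 95% margin on the ratio = exp(1.96 × 0.087) = about 1.19-fold.

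Against type-naive women, 1.07 and 1.14 lie inside this margin and 1.25 outside. Against women negative for both 16 and 18 (at most 1,275 × 0.72 = 918), the margin is also about 1.19: 1.10 lies inside, 1.20 is at the edge and 1.36 is outside.

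**5. After restriction.** With both groups negative for the other types, the difference in share is 0 and the false ratio is 1.00 for any F. Removing HPV 18-positive women alone leaves (18 − 8)/18 = 56% of the HPV 16-positive women: 1,275 × 0.10 = about 128. Against 918, SE = 1.2 × √(1/127.5 + 1/918) = 0.113, a margin of about 1.25-fold.

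**The case against.** The strongest reply is that Section IV.C.3.b already deals with the cross-type question. Table 5 compares all-naive women with women naive for the summarised type and seropositive for one named other type only, which estimates F directly. Further models relate the Month 7 response to the other types' baseline titers, separately in women seronegative and seropositive for the type of interest, and to the number of other seropositive types. If Table 5 showed nothing, the worry about Table 2 would largely fall away.

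Much of this stands. A reader might infer that the plan has no means of detecting a cross-type effect, and that is not so for Table 2. However, the plan does not say that these results will adjust or qualify Table 2, and the own-type regression in IV.C.3.a has no term for other types. They do not cover Table 3 either: Table 5 requires PCR negativity for the summarised type, and the titer models split women by serostatus, not PCR status.

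It is also fair to say that the stated aim is to explore, that no threshold or test is attached, and that different restrictions can suit different questions. The figures in the working count seropositive and PCR-positive women together, so they only approximate the Table 2 and Table 3 groups, and they exist for the 16/18 pair alone. A reader might infer that types 6 and 11 must add to the distortion; the document gives no overlap for them.

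**Conclusion.** The point holds as a modest one. Under either comparator in Tables 2 and 3, a difference in Month 7 GMT mixes own-type and other-type status, and the plan does not tie its cross-type analyses to the reading of those tables.

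The size is unknown. The illustrative false ratios of 1.07 to 1.25 (type-naive) and 1.10 to 1.36 (all-naive) rest on two assumptions: that the 16/18 overlap of Section VII.A.1 applies to these groups, and that a cross-type effect of 1.25- to 2-fold exists. The lower values could not be told from sampling error. The document does not support saying that a bias is present, only that these tables could not exclude one.

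A reader might also infer that lot consistency or another formal conclusion is in doubt. It is not: these are exploratory, observational summaries, and no primary or secondary conclusion depends on them.

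**What to change.** For each of the four types in Tables 2 and 3, data permitting, add one row in which Group 1 is restricted by the footnote already used in Tables 4 and 5, and compare it with the all-naive group. State in Section IV.C.3.a that any own-type statement rests on that row, read together with Table 5. Keep the unrestricted rows as supportive.

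The cost is some SAP wording and eight table rows (four types × two tables). For Table 2 the restricted group is essentially the two Table 4 groups for that type combined, so little new definition is needed. The real price is precision: at most about 56% of the HPV 16-positive women remain, fewer once types 6 and 11 are also excluded, and the intervals widen accordingly. The restricted row also answers a narrower question, about women positive for that one type only, which is a further reason to keep the existing rows.
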